 - Urine specimens: Initial processing and storage for urine microbiome analyses in Europe (if funding permits; see 8.2).

Use of Amsel criteria: As noted in the introduction, one of the four Amsel criteria is the presence of vaginal discharge, and we may therefore miss asymptomatic cases of BV if we use the Amsel criteria instead of Nugent scoring. This is not a problem for the women themselves because asymptomatic BV is normally not treated, but it is a missed opportunity for this study. We will closely monitor our Amsel data in the beginning of the study (compare the Amsel data with the Nugent data), and if warranted, we may decide to only use the three laboratory Amsel criteria to guide enrolment and treatment decisions. In that case, BV by Amsel criteria would be defined as 2 of the 3 laboratory criteria throughout this protocol.

6.5 Follow-up visits Day 7, Month 1 and Month 2

Follow up visits in the clinical trial will take place at Day 7 (7 days after start of the intervention), Month 1, Month 2 (cessation of the intervention), and Month 6 (4 months after cessation of the intervention).

The following procedures will take place during the Day 7, Month 1 and Month 2 follow up visits:

- 1. Confirmation of contact information. Women who are menstruating at the time of a study visit will be asked to return for completion of visit procedures after they have finished menstruating.
- 2. Face-to-face interview (update since the last study visit on: current medications, contraception, genital symptoms, sexual behaviour, vaginal practices, penile hygiene practices of male partners, having been diagnosed and/or treated for STIs/BV/vaginal candidiasis or other medical conditions, adverse events/social harms, and acceptability of and adherence to the interventions).
- 3. Speculum examination with collection of specimens: vaginal specimens for vaginal pH, wet mount, Gram stain Nugent scoring, TV culture and VMB and biofilm assessments at UoL, and a CVL to store for additional VMB assessments at UoL. If the participant has signs or symptoms of a reproductive tract infection, specimens will be collected for diagnostic testing as described for the screening visit.
- 4. Counselling with as main aim to address any questions or concerns the participant may have about her intervention. At the Month 2 visit, the intervention will be terminated.
- 5. Reimbursement, and scheduling of the next visit;

- 6. Participant leaves the RU clinic;

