2. To determine preliminary	- Incidence of the following STIs between screening and Month
efficacy of the three biomedical	6: HIV, HSV-2, syphilis, CT and NG
interventions compared to the	 Incidence of UTI between screening and Month 6
control group in reducing the	
incidence of STIs and UTI.	

3. Participant flow

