8.1 Incidence and incidence rate ratios of secondary efficacy outcomes

It has been hypothesised that a lactobacilli-dominated VMB would protect women from HIV, other STIs, and UTIs, and would facilitate pregnancy. While the sample size of this study was too small to adequately test these hypotheses, we did include incidence of HIV, STIs (other than TV), UTIs, and pregnancy as secondary outcomes. Women were tested for HIV and STIs (HSV-2, syphilis, CT, and NG) at the Screening and M6 visits, and for UTI and pregnancy at the Screening, Enrolment and M6 visits. In all cases, additional testing may have been done at the D7, M1 and M2 visits when clinically indicated. Incidence of these secondary outcomes will be determined between baseline (using endpoint data from the Enrolment visit if available and otherwise from the Screening visit) and M6.

Incident cases will be defined as follows:

- HIV: a positive result for the HIV serology algorithm at M6. Women who were HIV-positive at Screening were excluded from the study; therefore, all positive results at M6 will be treated as incident cases. Time at risk will start at the Enrolment visit.
- HSV-2: a positive result for HSV-2 serology at M6. Only those participants who tested negative for HSV-2 at Screening were retested at M6; therefore, all positive cases at M6 will be treated as incident cases. Time at risk will start at the Enrolment visit.
- Syphilis: a positive result for the syphilis serology algorithm at M6. All participants positive for syphilis at Screening were adequately treated prior to randomisation; therefore, all positive cases at M6 will be treated as incident cases. Time at risk will start at the Enrolment visit.
- NG: a positive result for NG PCR at M6 after a negative NG PCR result at Screening (time at risk will start at the Enrolment visit) or after having been successfully treated for NG during follow-up (time at risk will start on the treatment completion date).
- CT: a positive result for CT PCR at M6 after a negative CT PCR result at Screening (time at risk will start at the Enrolment visit) or after having been successfully treated for CT during follow-up (time at risk will start on the treatment completion date).

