- UTI: a positive urinalysis result (according to the Rwandan guidelines) at M6 or earlier during follow-up if tested due to symptoms after a negative urinalysis dipstick result at an earlier visit or after adequate UTI treatment. Time at risk will always start at the Enrolment visit because all UTI's at the Screening and Enrolment visits were treated prior to randomisation.
- Pregnancy: a positive urine pregnancy test at M6 (or earlier during follow-up). As being pregnant at Screening or Enrolment was a reason for exclusion in this study, all positive results will be treated as incident cases.

Incidence rates: IRs will be calculated as the number of incident cases per person-days (PD) of follow-up with 95% confidence intervals using the IR function in STATA. IRs will be calculated for each primary endpoint in each of the 4 randomisation groups and for the entire study population. In all cases, IRs will be calculated for the entire follow-up period as described above.

	Group 1		Group 2		Group 3		Group 4		Total	
	n/N ¹	Cases/PD (IR, 95% CI) ²	n/N¹	Cases/PD (IR, 95% CI) ²	n/N¹	Cases/PD (IR, 95% CI) ²	n/N¹	Cases/PD (IR, 95% CI) ²	n/N¹	Cases/PD (IR, 95% CI) ²
HIV										
HSV-2										
Syphilis										
NG										
СТ										
UTI										
Pregnancy										

1. Number of women (n) who developed at least one incident infection during the specified time period as a proportion of the women who completed all follow-up visits in that time period (N).

2. Incident rate (IR): Number of incidence cases per person-days of follow-up, with 95% confidence intervals (CI).

Incidence rate ratios (IRRs) with 95% confidence intervals will be calculated comparing each product use group (groups 2-4) to the control group (group 1) using the IR function in STATA. In addition, IRRs with 95% confidence intervals will be calculated comparing each vaginal probiotic group (group 3 and 4) to the metronidazole group (group 2). As before, these IRRs will be calculated for each primary efficacy outcome for the entire follow-up period.

	Group 2 vs 1 IRR (95% CI)	Group 3 vs 1 IRR (95% CI)	Group 4 vs 1 IRR (95% CI)	Group 3 vs 2 IRR (95% CI)	Group 4 vs 2 IRR (95% CI)
HIV					
HSV-2					
Syphilis					
NG					
СТ					
UTI					
Pregnancy					

The number of incident infections will likely be too small to allow for per-protocol analyses and GEE models as described for the primary efficacy outcomes in 6.3 and 6.4.

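### SAP 8.1 counts a gonorrhoea or chlamydia case only if PCR is positive at Month 6, so an infection found, treated and cleared earlier drops out of an endpoint declared as incidence from screening to Month 6

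*SAP*

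**What the plan says.** SAP section 2 declares the secondary endpoint as "Incidence of the following STIs between screening and Month" 6, and SAP 8.1 says incidence is determined between baseline and M6. The case definitions that follow in SAP 8.1 are:

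- Gonorrhoea (NG): "NG: a positive result for NG PCR at M6 after a negative NG PCR result at Screening", with a second route, "or after having been successfully treated for NG during follow-up (time at risk will start on the treatment completion date").
- Chlamydia (CT): "CT: a positive result for CT PCR at M6 after a negative CT PCR result at Screening", with the same second route.
- Syphilis: "Syphilis: a positive result for the syphilis serology algorithm at M6".
- HIV and HSV-2: positive serology at M6.
- UTI: a positive dipstick "at M6 or earlier during follow-up if tested due to symptoms". Pregnancy likewise accepts a positive test before M6.

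On testing before M6, SAP 8.1 says "additional testing may have been done at the D7, M1 and M2 visits when clinically indicated". Protocol 6.5 says that if a woman has signs or symptoms of a reproductive tract infection at Day 7, Month 1 or Month 2, "specimens will be collected for diagnostic testing as described for the screening visit". Protocol 6.8 and SAP 3.4 foresee unscheduled visits for suspected STIs. The opening of Protocol section 6 provides for treatment of syphilis, NG and CT at every visit.

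**The concern.** A negative PCR followed by a positive one is an incident infection, but for NG and CT the plan recognises it only if the positive result is the one at M6. Testing before M6 leads to treatment, and treatment makes the M6 result more likely to be negative. The rule therefore tends to remove symptomatic, treated infections and keep those still present at M6.

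Two things are at stake. The pilot is meant to inform the design of an efficacy trial whose long-term aim includes fewer HIV and other STIs, and an undercount labelled as incidence would mislead that work. The loss could also differ by arm, because interim testing depends on signs and symptoms, and neither participants nor study clinicians are blinded.

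**Working it through.** The documents state no STI incidence, power or sample-size figure for this endpoint, so there is no planned figure to reproduce. The check is to apply the written definitions to typical histories.

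**Histories under SAP 8.1**

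1. NG- or CT-negative at Screening, PCR-positive at M1, treated, negative at M6: 0 cases. Under the wording used for UTI and pregnancy she would be 1 case. The second route in the NG and CT definitions does not help her. It only restarts time at risk, and the case itself must still be an M6 positive.
2. As above, but reinfected and positive at M6: 1 case, not 2. Time at risk is ambiguous, because she meets both the Screening-negative condition (start at Enrolment) and the treated condition (start at treatment completion). For the primary outcomes, SAP 6.1 counts every incident infection in a woman.
3. Syphilis found and treated before M6: lost only if the algorithm (haemagglutination with RPR confirmation, SAP 4.1) is negative again at M6. If it is still positive, she is counted.
4. HIV or HSV-2 seroconversion found before M6: neither is in the list of curable infections treated at the clinic. M6 testing is planned for HIV in all women and for HSV-2 in all who were negative at Screening. Assuming the antibody result persists, she is counted at M6 unless she misses that visit. SAP 3.1 gives 64 attending M6, and 68 − 64 = 4.

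**Illustration of scale (all case counts assumed)**

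Take 17 women per arm and about 182 days each: 17 × 182 = 3,094 person-days per arm, equal between arms. With a cases in the product arm and b in the control arm, IRR = a/b. The exact 95% interval takes the Clopper-Pearson limits p for a out of a + b and converts them by p/(1 − p).

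| Situation | Product | Control | IRR (95% CI) |
|---|---|---|---|
| All infections counted | 2 | 4 | 0.50 (0.05 to 3.49) |
| One control case cleared before M6 | 2 | 3 | 0.67 (0.06 to 5.82) |
| Two control cases cleared before M6 | 2 | 2 | 1.00 (0.07 to 13.8) |
| One product case cleared before M6 | 1 | 4 | 0.25 (0.01 to 2.53) |

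In the control arm, going from 4 cases to 3 lowers the rate from 4/3,094 × 36,525 = 47.2 to 3/3,094 × 36,525 = 35.4 per 100 person-years, a quarter less. One or two lost cases move the rate ratio anywhere between 0.25 and 1.00, and every interval remains very wide.

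**The case against.** The best defence is that M6 is the only STI test after randomisation that every woman is scheduled to have, with laboratory staff blinded. Interim testing is symptom-driven and open-label. A product that causes discharge or itching would lead to more tests and so more detected cases, and adding those cases could bias the comparison. That stands as a reason to show the M6-only count. It does not make the M6-only rule safe, because treatment after an interim test changes the M6 result. The rule keeps the dependence on symptoms and discards the cases as well.

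It is also fair that treated infections are not invisible. SAP 6.1 describes antibiotic use by indication and SAP 3.4 tabulates visits for STI testing. Neither enters the incidence rate.

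It also stands that this is a secondary endpoint, which the SAP itself says the sample is too small to test.

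A reader might infer that all five infections lose every case found before M6. The documents do not support that: serology is repeated at M6 for HIV and HSV-2, and the loss for syphilis is conditional. Protocol 6.9 also asks women who withdraw after Month 2 to complete the Month 6 procedures, although the SAP does not say whether those results count as M6.

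A reader might also take the 26 of 68 women with CT or NG when randomised (8 + 7 + 4 + 7, SAP 6.3) as the size of the loss. That figure is infection already present at Screening. It says nothing about how many new infections were found before M6.

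**Conclusion.** The concern holds for NG and CT. Read literally, the definitions drop an infection in a Screening-negative woman that is found, treated and cleared before M6. This contradicts both the declared endpoint and the handling of UTI and pregnancy in the same section, and nothing else in either document repairs it.

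For syphilis the loss depends on the serology algorithm being negative again at M6. For HIV and HSV-2 it is confined to women diagnosed early who have no M6 result, at most 4 of 68, on the assumption that antibody persists.

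The actual number of lost cases is unknown because interim positives are not reported, and the direction of any bias between arms is not fixed. The rate ratios in the illustration rest on invented counts and equal person-time. They show only how sensitive such small numbers are. The change is worth making because it is cheap and corrects a stated rule that miscounts incidence.

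**What to change.** In SAP 8.1:

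- **NG and CT:** replace the M6-only condition with a positive PCR at M6 or earlier during follow-up, at a scheduled or unscheduled visit. Keep the existing requirement of a negative Screening PCR or successful treatment, so that infections persisting from Screening are not counted as new.
- **Time at risk (NG and CT):** for Screening-negative women, start at Enrolment, stop at the first positive test and restart at treatment completion.
- **Syphilis:** use the same wording, but do not count an interim positive that reflects persisting serology from an infection treated at Screening.
- **HIV and HSV-2:** allow an earlier positive to count for women without an M6 result.
- **Early positives:** flag those, such as at Day 7, that may pre-date randomisation. Screening may take up to 6 weeks, so a negative Screening test can be well before Enrolment.
- **Reporting:** show the M6-only case count by arm beside the total.

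The cost is revised wording and one extra table column, using results already collected. The small downside is that the added cases come from symptom-driven, open-label testing, which is why the M6-only count should stand next to them.

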4.4 Randomisation and blinding

Participants will be randomised at the enrolment visit. Study group allocation will be concealed until the participant was confirmed to be eligible and has provided written informed consent for enrolment. Computer-generated group allocations will be generated prior to study initiation and concealed in randomisation envelopes numbered 1-60. The envelopes will be opened in consecutive order as new participants are randomised. The study clinicians cannot be blinded because the study products look different and dosing schedules are different. However, we will blind the laboratory technicians at RU and at UoL so that the assessment of all laboratory endpoints is blinded. This will be achieved by ensuring that study samples and accompanying documents that are shared with the laboratory technicians do not contain any information about the study arm that the participant was randomised to.

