3.4 Numbers of and reasons for unscheduled visits

Time period	Number of women	Number of visits
Between the Screening and Enrolment visits (not including		
Results visits scheduled by RU staff)		
Between Enrolment and M1		
Between M1 and M2		
Between M2 and M6		
After M6		
TOTAL		

Reasons for unscheduled visits	Number of visits
To withdraw informed consent	
To obtain additional study product supplies	
To report an (S)AE or social harm	
To test for an STI or vaginal infection	
To test for a UTI	
To collect treatment for a positive lab result	
Wants to be tested for HIV or pregnancy	
For male partner HIV/STI testing and couple counselling	
To ask questions or express concerns	
Other (each reason will be listed)	
TOTAL	

4. Analyses of baseline data

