2. Kehua HIV Rapid Test (Kehua Bioengineering Co., Shanghai, China) with Determine HIV Rapid Test (Abbott Laboratories, Tokyo, Japan) for confirmation of positive results and the Unigold HIV Rapid Test (Trinity Biotech Plc, Bray, Ireland) as tie-breaker.

3. Nova hCG urine pregnancy test (Nova, Waltham, USA).

4. Nova urinalysis dipstick test (Nova, Waltham, USA), considered UTI-positive if nitrites were positive or at least 1+ leucocytes (in

accordance with Rwandan guidelines).

- 5. The modified Amsel score was positive if 2 or 3 of the following criteria were positive: 1) >20% clue cells on wet mount 2) a positive KOH (amine) test; 3) vaginal pH > 4.5.
- 6. Spinreact *T. pallidum* Haemagglutination test with confirmation of active infection by Spinreact Rapid Plasma Reagin test (Spinreact, Girona, Spain).
- 7. Kalon HSV-2 test (Kalon, Guildford, United Kingdom), with optical density (OD) > 1.1 of the mean OD of the cut-off defined as positive) and < 0.9 of the OD of the cut-off defined as negative.

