7.3 Adverse events: structurally assessed at each study visit

Some safety outcomes were structurally assessed at each study visit as part of the face-to-face interview and pelvic and bimanual examination. Laboratory test results will not be included because they are covered under the primary and secondary efficacy outcomes. The safety outcomes will be reported as the number of women who experienced the event at least once during the time period by study group. Differences between the randomisation groups will be assessed by Fisher's exact test. If the p-value is < 0.05, pairwise comparisons (also using Fisher's exact test) between study groups will be conducted. If an AE occurred more than once in individual women, the analysis will be repeated for the number of events (as opposed to number of women) per study group. All analyses will be done for three time periods: between the Enrolment and M2 visits (during product use), between the M2 and M6 visits (after cessation of product use), and for the overall follow-up period between the Enrolment and M6 visits.

Number of women	Group 1	Group 2	Group 3	Group 4	p-
Between Enrolment – M2	N=17	N=17	N=17	N=17	value ¹
Any patient-reported urogenital symptoms (n %)					
If yes, symptoms reported (n % for each) ² :					
– Burning when passing urine					
 Frequent urination or urgent need to urinate 					
– Blood in urine					
– Genital burning					
– Genital itching					
– Pain during sex					
– Lower abdominal pain					
– Unusual vaginal discharge					
– Sores in the genital and/or anal area					
(including buttocks)					
– Other (describe in footnote)					
Any abnormal findings during pelvic exam					
clinician-observed (n %)					
If yes, findings observed (n % for each) ² :					
– Abnormal (genital) odour					
 Enlarged/tender inguinal lymph node 					
 Condylomata (any location genitalia) 					
 Ulcers/blisters suggestive of STI on vulva 					
 Any other lesion on vulvar epithelium 					
 Abnormal vaginal discharge 					
–Vaginal mass (polyp, myoma, etc.)					
 Ulcers/blisters suggestive of STI in vagin 					
 Any other lesion on vaginal epithelium 					
 Abnormal cervical discharge/pus 					
 Any lesion on cervical epithelium 					
 Other (describe in footnote) 					
Any abnormal findings during bimanual exam					
clinician-observed (n %)					
If yes, findings observed (n % for each) ² :					
– Uterine mass					
– Adnexal mass					
- Uterine tenderness					
– Adnexal tenderness					

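### The UTI rate ratio in SAP 8.1 adds symptom-triggered dipsticks to the scheduled Month 6 dipstick, so it can move away from 1 if testing frequency differs between arms

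*SAP*

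**What the plan says.** **Testing schedule.** SAP 8.1 says women were tested "for UTI and pregnancy at the Screening, Enrolment and M6 visits", and that "additional testing may have been done at the D7, M1 and M2 visits when clinically indicated". M6 is therefore the only scheduled UTI test after randomisation. The schedules in Protocol 15.2 and SAP Table 1 agree: the dipstick is bracketed at D7, M1 and M2. SAP 3.4 also lists "To test for a UTI" among the reasons for unscheduled visits, in a table that is not split by arm.

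**Case definition and analysis.** SAP 8.1 defines incident UTI as "a positive urinalysis result (according to the Rwandan guidelines) at M6 or earlier during follow-up if tested due to symptoms", following an earlier negative dipstick or adequate treatment. Time at risk starts at Enrolment. The rate is cases per person-day, and the IRR table has a UTI row with five comparisons (2 v 1, 3 v 1, 4 v 1, 3 v 2, 4 v 2).

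**Threshold.** Under SAP 4.1, footnote 4, a dipstick is "considered UTI-positive if nitrites were positive or at least 1+ leucocytes".

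**Blinding.** Protocol 4.4: "The study clinicians cannot be blinded because the study products look different and dosing schedules are different". The same section adds that "we will blind the laboratory technicians at RU and at UoL so that the assessment of all laboratory endpoints is blinded".

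**Safety tables.** SAP 7.3: "Laboratory test results will not be included because they are covered under the primary and secondary efficacy outcomes". Dipstick-defined UTI is therefore compared between arms in SAP 8.1 and not in the structured safety tables.

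**The concern.** The design does not fix the number of dipsticks per woman. Everyone is due one at M6; anything earlier depends on symptoms being reported and a clinician acting on them. The denominator is person-days, which stay the same however many tests are done. An arm with more tests has more chances to score a case over the same time at risk.

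The plan itself allows that symptoms may differ by arm. SAP 7.3 compares burning on urination, frequency, genital burning and discharge between groups. The Gynophilus insert in Protocol 15.3 warns of discharge after insertion. Protocol 6.8 encourages women to attend between visits for events they suspect are product-related, a reason that has no counterpart in the control group. The leucocyte-only threshold could also let a dipstick prompted by non-urinary irritation count as a UTI; that step is an inference and is not stated in the documents.

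SAP 8.1 handles the infections in the same table differently. HIV, HSV-2, syphilis, NG and CT are each defined on the M6 result. Only UTI and pregnancy also count earlier results.

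At stake is the point estimate. Protocol 3.2 says the pilot's data are needed to choose interventions and design the efficacy trial, so a UTI ratio that partly measures testing could be misread as a harm or a benefit.

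**Working it through.** The documents give no UTI rate, effect size or testing rate, so there is no figure to reproduce. The calculation below shows how far the ratio could move with no true effect.

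**From the documents:** one dipstick at M6 for all women; three interim visits with a dipstick only if indicated; 17 women per arm (SAP 4.2); M6 attendance 64 of 68, or 94% (SAP 3.1).

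**Assumed:** each dipstick is positive with the same probability *p* in both arms; a fraction *a* of control women and *b* of product women are tested at each interim visit; person-days are equal; each positive counts as a case; unscheduled visits are ignored.

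Expected cases per woman are *p*(1 + 3*a*) in control and *p*(1 + 3*b*) in the product arm, so the expected ratio is (1 + 3*b*)/(1 + 3*a*), and *p* cancels.

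| *a* | *b* | Calculation | Null IRR |
|---|---|---|---|
| 5% | 10% | 1.30/1.15 | 1.13 |
| 10% | 20% | 1.60/1.30 | 1.23 |
| 5% | 20% | 1.60/1.15 | 1.39 |
| 10% | 30% | 1.90/1.30 | 1.46 |
| 30% | 30% | 1.90/1.90 | 1.00 |

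Counting the M6 dipstick alone gives *p*/*p* = 1.00 whatever *a* and *b* are.

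**Sensitivity to equal positivity.** Take the 10% v 30% case, where the product arm has 3 × 0.20 = 0.60 extra tests per woman. If those extra tests are positive at a multiple *f* of the routine rate, the ratio is (1.30 + 0.60*f*)/1.30:

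- *f* = 0: 1.00
- *f* = 0.5: 1.60/1.30 = 1.23
- *f* = 1: 1.46
- *f* = 2: 2.50/1.30 = 1.92

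**Scale at 17 per arm.** With 10% v 30% testing and *p* = 0.10, expected cases are 17 × 0.10 × 1.3 = 2.2 and 17 × 0.10 × 1.9 = 3.2. In a simulation of 200,000 trials with no true effect, the more-tested arm had more UTI cases in 59% and fewer in 25%. Counting M6 only, the figures were 38% and 38%. An exact conditional test gave p<0.05 in 1.5% of trials; in the most extreme setting tried (10% v 50% testing, *p* = 0.20) it did so in 11.5%. The effect is mainly a shift in the point estimate.

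**The case against.** The strongest reply is that this is a possible bias that nobody has shown to occur. A reader might infer that the arm with more irritation will be tested more and will appear to have more UTI. The documents do not support that: they give no symptom or testing rates by arm, and equal testing leaves the null ratio at 1.00. Nor does irritation from a vaginal product explain the Group 2 v 1 comparison, because Group 2 as analysed took oral metronidazole (SAP 1.1). This stands, and the point is conditional.

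A reader might also infer that unblinded staff read the strips. Protocol 8.1 places the dipstick in the onsite laboratory, and Protocol 4.4 blinds its technicians. Only the decision to test, and the symptom report behind it, is open. This stands too.

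Third, the plan already gives context. SAP 7.3 reports urinary and genital symptoms by arm for each period; SAP 7.4 codes and reports newly reported conditions by arm; SAP 6.1 describes antibiotic use by indication. It would be wrong to say that 8.1 holds all the information on UTI. None of these, however, gives the number of dipsticks done by arm, which is the missing piece.

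Fourth, the stated endpoint is UTI incidence between screening and Month 6 (SAP 2). Comparing arms on M6 alone would replace incidence with a single reading four months after product use, and would drop symptomatic UTI during product use from the comparison. More testing in an arm may also reflect more genuine symptomatic UTI. This stands against replacing the combined count. It does not count against showing its two sources separately.

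Finally, UTI is a secondary outcome in a pilot that SAP 8.1 itself describes as too small to test these hypotheses. That limits the importance of the point.

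**Conclusion.** The concern holds in conditional form. The UTI row pools a scheduled test with symptom-triggered tests, divides by person-days, and plans neither an M6-only comparison nor a count of tests by arm. If symptom-driven testing differs between arms, the IRR can depart from 1 with no difference in infection.

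Under the unequal testing rates in the table and equal positivity per test, the null IRR runs from 1.13 to 1.46. Those rates are assumptions, and relaxing equal positivity moves the 10% v 30% figure anywhere from 1.00 to 1.92 for the multiples shown. Neither the direction nor the presence of a bias in this trial can be read from the documents. A false significant result is unlikely at this sample size, so the consequence is a point estimate that cannot be interpreted without the testing counts. This is a minor but worthwhile improvement to one secondary table.

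**What to change.** Keep the combined incidence count in SAP 8.1, since it matches the stated endpoint, and state that its IRR is descriptive and sensitive to ascertainment. Then split the UTI row by source:

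- **(a) Scheduled M6 dipstick:** positives over women tested, by arm, with a between-arm risk difference and exact interval. This comparison does not depend on how often women were tested earlier.
- **(b) Symptom-triggered UTI (D7 to M2 and unscheduled visits):** positives by arm, with the number of women tested and the number of tests beside them.

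Separating nitrite-positive cases within each row is optional.

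The cost is two more table rows and no new samples, provided each interim dipstick is recorded whatever its result. The drawback is that row (a) describes UTI four months after product use, so UTI during product use has to be interpreted from row (b).
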